**8. Subject Safety Monitoring:**

Subjects, both patients and healthy controls, are monitored by one of the associate investigators during all study procedures. Medical history and physical assessments occur at each clinic visit including interviews, symptom assessments, vital signs, and laboratory testing when clinically indicated.

As the population being studied in this protocol may be at high risk to develop subsequent depressions and as gonadal steroids have been implicated in the etiology of

postpartum depression, some depressive reactions may occur during this protocol. However, based on experience with Lupron and estradiol/progesterone addback in women with menstrually-related mood disorders and preliminary observations of 16 women participating in this protocol, we would expect mood symptoms to be of mild severity. Adverse mood symptoms will be monitored by administering the Beck Depression Inventory (BDI); if BDI scores of > 20 are observed at any period in the protocol then the Hamilton Rating Scale for Depression will be administered on consecutive days. Anyone scoring > 20 on the Hamilton for three or more consecutive days, or any subject with suicidal ideation, or anyone with concerns about their ability to continue in the study, will be considered to have severe mood symptoms and be discontinued from the protocol. In the event of the occurrence of severe mood symptoms, either the protocol will be terminated, or if symptoms occur during the withdrawal phase, hormone replacement will be re-instituted. Should this step prove to be unsuccessful, conventional medication will be prescribed as needed. Further, although we do not anticipate severe adverse reactions, we have arranged for inpatient hospital admission at the Clinical Center if symptoms are otherwise unmanageable.

Criteria for individual subject withdrawal:

Any subject requiring immediate treatment will be referred for private treatment. In the event that private treatment cannot be arranged promptly, the subject will be treated openly with an antidepressant until successful referral can be achieved.

Subjects presenting as “healthy” but found to have a psychiatric diagnosis will be discharged from this protocol and either be referred to the community for further evaluation and treatment or consented to another NIMH protocol. In the case a psychiatric diagnosis is unveiled; the assessment and disposition plan will be reviewed with a senior clinician who reviews the case with the [name].

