**10. Statistical Analysis:**

Analysis of Data: A repeated measures design has four groups of ten subjects each for a total of forty subjects. Each subject is measured during the hypogonadal baseline, at the end of the two months of addback, and during the following month (i.e., continued addback in group 2 or withdrawal in group 1). The effect of hormonal addback and withdrawal in subjects and controls on mood and biological parameters will be calculated using ANOVA-R with post-hoc Bonferroni t-tests.

Sample Size Justification: Based on previous data (61), the between-subject standard deviation is 0.69 and the within-subject standard deviation is 0.28. This design achieves 67% power when an F test is used to test the Groups factor at a 5% significance level and the actual standard deviation among the appropriate means is 0.30 (an effect size of 0.43), achieves 81% power when an F test is used to test the Times factor at a 5% significance level and the actual standard deviation among the appropriate means is 0.16 (an effect size of 0.57), and achieves 60% power when an F test is used to test the group by time interaction at a 5% significance level and the actual standard deviation among the appropriate means is 0.13 (an effect size of 0.46).

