**11. Human Subjects Protection:**

Subject selection:

All subjects must meet the inclusion and exclusion criteria listed in Section 3. We will select physically healthy adult female individuals. The proportion of ethnic minorities (vs. Caucasians) in the total sample, will be approximately consistent with the overall U.S. population proportions.

Justification for inclusion/exclusion of children:

We will exclude children or minors because the study population is women with postpartum depression.

Justification for symptom challenge procedure:

The justification for employing a symptom challenge is three-fold as follows:

a. The study of PPD is very difficult because of pharmacologic limitations and child care constraints. A hormonal model of pregnancy and parturition may help overcome some of these difficulties.

b. The development of mood and behavior symptoms in this study may predict psychiatric problems in future pregnancies and may suggest a subgroup of women with an affective disorder who are differentially susceptible to the hormonal changes of pregnancy and parturition.

c. This model may be helpful in understanding underlying biological mechanisms in depression and affective disorders in general.

Safeguards: As described above in the Subject Safety Monitoring: Adverse mood symptoms will be monitored by administering the Beck Depression Inventory (BDI); if BDI scores of > 20 are observed at any period in the protocol then the Hamilton Rating Scale for Depression will be administered on consecutive days. Anyone scoring > 20 on the Hamilton for three or more

consecutive days, or any subject with suicidal ideation, or anyone with concerns about their ability to continue in the study, will be considered to have severe mood symptoms and be discontinued from the protocol. In the event of the occurrence of severe mood symptoms, either the protocol will be terminated, or if symptoms occur during the withdrawal phase, hormone replacement will be re-instituted.

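### Section 10 does not say which month-5 value is analysed when a woman is stopped, or has hormones re-started, for severe mood symptoms; triggers in the withdrawal arm would pull the key contrast toward zero by an unknown amount, possibly nil

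*Combined protocol and SAP*

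**What the plan says.** **Safety rule (section 8, largely repeated in section 11).** The check starts "if BDI scores of > 20 are observed at any period in the protocol"; the Hamilton is then given on consecutive days. A woman scoring above 20 on the Hamilton for three or more consecutive days, or with suicidal ideation, or with concerns about continuing, "will be considered to have severe mood symptoms and be discontinued from the protocol". The next sentence gives termination as one course, but says that "if symptoms occur during the withdrawal phase, hormone replacement will be re-instituted"; section 11 repeats the pair: "either the protocol will be terminated, or if symptoms occur during the withdrawal phase, hormone replacement will be re-instituted". Section 8 adds conventional medication if re-start fails. Under its withdrawal criteria it says that, where prompt referral is not possible, "the subject will be treated openly with an antidepressant until successful referral can be achieved".

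**Expected severity.** Section 8 says "we would expect mood symptoms to be of mild severity". Section 4e reports that emergent symptoms were mostly mild to moderate and time-limited. No count or rate of women meeting the criterion is given.

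**Outcomes (section 9).** The Beck and Hamilton scales are among the listed outcome measures.

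**Analysis (section 10).** "Each subject is measured during the hypogonadal baseline, at the end of the two months of addback, and during the following month". Effects "on mood and biological parameters will be calculated using ANOVA-R with post-hoc Bonferroni t-tests". No rule is stated for a missing third value, or for one recorded after re-started hormones or an antidepressant.

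**The contrast that matters (section 4d).** The arms differ only in the fifth month of Lupron, when one is withdrawn from estradiol and progesterone and the other continues.

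**The concern.** Sections 1b and 2 explain that the randomised design was introduced to separate withdrawal from prolonged exposure. Month 5 is the only place where the arms differ, so everything rests on the month-5 value.

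The safety text can be read in two ways. A woman may be discontinued and then receive care, which leaves month 5 missing. Or she may have hormones re-started in place of termination, so that month 5 is recorded under the comparator's exposure. Section 10 covers neither case. Because the criterion is a score on an outcome scale, loss or replacement of the value depends on the outcome itself, and the re-start provision operates only in the withdrawal phase. If the most symptomatic withdrawal-arm women vanish from the contrast, or are counted after relief, the result drifts toward a conclusion that withdrawal adds nothing to prolonged exposure.

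**Working it through.** **1. Inputs from section 10.** Four groups of 10, three times, between-woman SD 0.69, within-woman SD 0.28, SD of interaction means 0.13. Stated power: Groups 67%, Times 81%, interaction 60%.

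**2. The plan's own figures.** Noncentral F, λ = N·f² with N = 40:

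| Test | λ | df | Computed | Stated |
|---|---|---|---|---|
| Groups | 40·(0.30/0.69)² = 7.56 | 3, 36 | 57.5% | 67% |
| Times | 40·(0.16/0.28)² = 13.06 | 2, 72 | 89.7% | 81% |
| Interaction | 40·(0.13/0.28)² = 8.62 | 6, 72 | 52.5% | 60% |

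The stated figures do not reproduce. Two groups of 16 at three times give 66.3%, 81.3% and 62.5%, which is closer. That is a separate matter, but it makes the next step an assumption.

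**3. Assumed true difference.** The plan states no month-5 difference. If the interaction SD of 0.13 comes from one raised cell:
- 4×3 table: 0.13/√(¾·⅔/12) = 0.637
- 2×3 table: 0.13/√(½·⅔/6) = 0.55

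The illustration uses 0.637.

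**4. Model.** 10 women per arm. Addback = woman effect + error. Month 5 = woman effect + 0.637 (withdrawal) or + 0 (continuation) + error. The contrast is the difference in mean change. The k highest month-5 scores in the withdrawal arm trigger.

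**5. Closed form.** The woman effect cancels in the change, so only the error part of a high score matters. Its share of the variance is 0.28²/(0.69² + 0.28²) = 0.0784/0.5545 = 0.141, and the SD of the month-5 score is √0.5545 = 0.745. The expected top three of ten standard normal values are 1.538, 1.001 and 0.656 (mathematical constants). The summed excess error of the triggered women is E = 0.141 × 0.745 × (sum of the top k) = 0.162, 0.267, 0.336 for k = 1, 2, 3.
- Dropped: 0.637 − E/(10 − k)
- Scored after full relief: 0.637 − (k·0.637 + E)/10

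| k of 10 | Dropped | Loss | Full relief after re-start | Loss |
|---|---|---|---|---|
| 0 | 0.637 | 0 | 0.637 | 0 |
| 1 | 0.619 | 3% | 0.557 | 13% |
| 2 | 0.603 | 5% | 0.483 | 24% |
| 3 | 0.589 | 8% | 0.412 | 35% |

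A simulation of 40,000 trials per setting agrees to within 0.001. It puts power at 92% without triggers, 89/86/81% with women dropped and 82/67/51% after full relief. With half relief the contrast is 0.59/0.55/0.51. With re-start but no relief it is 0.62/0.61/0.60.

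**6. The other arm.** Dropping the 1, 2 or 3 highest scorers from the continuation arm instead raises the contrast to 0.655, 0.671 or 0.685.

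**7. Does a pre-rescue score repair it?** Assume two month-5 visits, a trigger at the first, and that score used:
- Full effect already present: 0.65/0.66/0.67, slightly high because the score was selected for being high.
- Half the effect present: 0.62/0.60/0.58, much like dropping.

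If there is no pre-rescue score, a mixed model alone gives 0.61/0.59/0.57.

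**The case against.** **Triggers may be rare or absent.** Section 8 expects mild symptoms and section 4e reports mostly mild to moderate ones, so 10–30% of women crossing the Hamilton threshold is pure assumption. This stands, and is why the size is left open with nil included. Section 7's statement that no adverse reactions occurred covers only the 25 women who completed, so it gives no rate either.

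**The text may favour simple discontinuation.** If re-start is care given after a woman has left the protocol, the loss is the dropped column, 3–8%. That is a fair reading, but the sentence offering re-start as the alternative to termination allows the other. The documents do not settle it.

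**Larger losses.** A reader might infer attenuation of 40% or more by letting women trigger on their change from addback. The documents do not support this: the only score criterion is an absolute Hamilton level. Larger losses under a level trigger need a further assumption. With responses varying between women by an SD of 0.6, dropping gives 0.56/0.49/0.43, but the plan states no such spread.

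**Direction.** A reader might infer that every trigger biases toward zero. That holds only for the withdrawal arm. The criterion applies in any phase, and step 6 shows that dropping continuation-arm women moves the estimate slightly the other way.

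**The BDI.** It prompts Hamilton ratings and does not itself stop a woman, so the overlap of criterion and outcome rests mainly on the Hamilton.

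**Conclusion.** The gap is real: two foreseen outcomes of the safety rule have no counterpart in the analysis of the one contrast that answers the trial's question. If withdrawal-arm women trigger, a true effect is attenuated. The amount is unknown and may be zero. Under the stated assumptions it is about 3–8% if they are dropped and 13–35% if they are scored after full relief. These figures rest on an assumed trigger count, assumed relief after re-start, and an assumed difference of 0.637 (0.55 on another reading of the same interaction SD). None is a figure of the plan.

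A reader might also infer that using pre-rescue scores removes the bias. Step 7 shows that it does not: the score may precede the full effect or be selected for being high, and it may be absent when the trigger was suicidal ideation or concern about continuing, since neither requires a score. Confidence is medium: firm on the missing rule and on the direction in the withdrawal arm, weak on size.

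**What to change.** The sponsor should reconcile the discontinuation and re-institution statements in sections 8 and 11; no clinical rule is proposed. In section 10:

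1. Define the month-5 value as the last scheduled month-5 ratings before discontinuation, hormone re-start or antidepressant treatment. Exclude later ratings from the withdrawal-versus-continuation estimate.
2. Replace the repeated-measures ANOVA with a likelihood-based mixed model on all scheduled scores, with every randomised woman in her assigned arm. A woman without a month-5 value then still contributes her earlier phases. Do not carry addback scores forward as month-5 values.
3. Add one sensitivity analysis: women stopped or re-started for severe mood symptoms receive the worst rank on change from end of addback to month 5, compared between arms by a rank-sum test on a mood scale that the sponsor names. Ranking change is preferable to ranking the raw month-5 score: power without triggers is 90% against 40% in the illustration.
4. Report triggers by arm, diagnosis and phase.

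**Cost.** SAP wording and a little more analysis work. The daily self-ratings and biweekly visits in section 4d already supply the data, so no visit or procedure is added. The bias is reduced, not removed, and the worst-rank analysis matters most where no pre-rescue score exists.

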**9. Outcome Measures:**

Outcome measures will include the scores on several standardized cross-sectional rating scales (Beck Depression Inventory, Hamilton Depression and Anxiety Scales, and Edinburgh Postpartum Depression Scale), symptom rating scales completed daily, plasma hormone measures (including neurosteroid levels and metabolomic profile), induced pluripotent cells and immortalized lymphoid cells mRNA expression after exposure to estrogen and progesterone withdrawal, and the response to the o-CRH stimulation tests.

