the minor depression module of the SADS-L. Urinary HCG will be determined to rule out pregnancy. Subjects who meet the inclusion criteria and who are medication free may be asked to return for follow-up interviews. During these interviews, phenomenological assessments may be performed by instruments such as the Premenstrual Tension Syndrome Scale (Steiner-Carroll Scale) (84), Beck Depression Inventory (85), Spielberger State-Trait Anxiety Inventory (86), Hamilton Rating Scales for Depression and Anxiety (87), Edinburgh Postnatal Depression Scale (88)) and related psychological measures. Additionally, subjects will be asked to fill out symptom self-rating scales, a modified version of the Daily Symptom Rating Form (Halbreich and Endicott) (89) and visual analogue scales (90), on a daily basis. During screening in protocol 81-M-0126 all subjects will receive a careful medical screening and will be excluded if there is evidence of significant renal, cardiac, hepatic, or other medical disorder. All patients will receive routine physical and laboratory examinations such as urinalysis, hematocrit, hemoglobin, BUN, creatinine, liver function tests, electrolytes, HIV, and a serum pregnancy test. Additionally, all women will have a normal EKG, and a normal PAP and gynecologic exam within the past year.

Subjects will be seen at the outpatient clinic on a regular biweekly basis. (Total = three baseline and 15 visits during treatment and follow-up.) During clinic visits, subjects will be monitored and managed for side effects, and blood samples will be drawn.

Research Procedures: Following the baseline period patients will receive 3.75 mg of the gonadotropin releasing hormone (GnRH) agonist leuprolide acetate (Lupron) during the early follicular phase of the menstrual cycle via intramuscular injection on a monthly basis in our clinic for five months. During the first two months of GnRH agonist administration, all subjects

will receive placebo progesterone and placebo estradiol tablets and will be told that at some point the placebo pills will be switched to active medication.

After the second month of Lupron-alone treatment, active estradiol and progesterone replacement will be initiated. Subjects shall be randomly assigned to one of two groups, and treatment shall be administered as follows:

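### No mood outcome or test is primary, error across at least five mood measures is uncontrolled, and the stated power is tied to no named outcome

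*Combined protocol and SAP*

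**What the plan says.** Section 9 (Outcome Measures) opens with "Outcome measures will include the scores on several standardized cross-sectional rating scales" and then lists "Beck Depression Inventory, Hamilton Depression and Anxiety Scales, and Edinburgh Postpartum Depression Scale), symptom rating scales completed daily". Plasma hormones, cell-line mRNA expression and the o-CRH response follow in the same sentence. Nothing in it is called primary or secondary, and no other section ranks the outcomes. Section 4 shows that the daily ratings are more than one instrument: a modified daily symptom form "and visual analogue scales (90), on a daily basis".

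Section 10 (Statistical Analysis) describes "four groups of ten subjects each for a total of forty subjects". On timing it says: "Each subject is measured during the hypogonadal baseline, at the end of the two months of addback, and during the following month". Effects on mood and biological parameters alike "will be calculated using ANOVA-R with post-hoc Bonferroni t-tests". No adjustment across outcomes is given.

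The sample size paragraph relies on a cited earlier study by the same group, from which "the between-subject standard deviation is 0.69 and the within-subject standard deviation is 0.28". It names no outcome and no unit. It then gives power at the 5% level of 67% for Groups, 81% for Times and 60% for the group-by-time interaction.

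The only information on the size of any mood score is in the safety rules of Sections 8 and 11. These act "if BDI scores of > 20 are observed at any period in the protocol" and use the same cut-off of 20 on the Hamilton depression scale.

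**The concern.** The trial asks whether women with past postpartum depression respond differently from controls, and whether withdrawal or prolonged exposure drives the symptoms. With five or six mood measures of equal standing and no primary test, a significant group-by-time result on any one of them could be presented as the answer. Each test is at 5%, but the set of tests is not. Groups of ten and a stated interaction power of only 60% make selective emphasis on one scale a real risk.

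The power statement does not repair this. If the outcome behind the standard deviations were named, it would be the natural primary. Because it is not, the stated power cannot be attached to any entry in Section 9.

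The sponsor did address multiplicity elsewhere: the RNA-sequencing plan in Section 1 specifies false discovery rate correction. The clinical outcomes have no counterpart.

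**Working it through.** **Inputs.** From Section 10: 4 groups × 10 women = 40, 3 times, between-subject SD 0.69, within-subject SD 0.28, SDs among means 0.30, 0.16 and 0.13. From Section 9: four named scales plus daily ratings, counted as five outcomes. From Section 8: the cut-off of 20 on the Beck and Hamilton scales. The documents give no correlation between outcomes, so a range is assumed.

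**1. The plan's own figures.** Effect size f = SD among means ÷ SD:

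- Groups: 0.30/0.69 = 0.43
- Times: 0.16/0.28 = 0.57
- Interaction: 0.13/0.28 = 0.46

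All three match Section 10. Power from the noncentral F distribution, with λ = N·f² and N = 40:

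| Test | df | λ | Power, λ = N·f² | Stated |
|---|---|---|---|---|
| Groups | 3, 36 | 7.56 | 57.5% | 67% |
| Times | 2, 72 | 13.06 | 89.7% | 81% |
| Interaction | 6, 72 | 8.62 | 52.5% | 60% |

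The powers do not reproduce. With λ = 3·N·f² (each woman counted at all three times) they become 97.7%, about 100% and 97.3%. No variant tried for 40 women and three times gave all three stated figures.

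**2. Error across outcomes.** If five interaction tests were independent, the chance of at least one false positive would be 1 − 0.95⁵ = 22.6%. The scales will be correlated, so the 4 × 10 × 3 ANOVA was simulated with no true effects, using SDs 0.69 and 0.28 and a common correlation between outcomes:

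| Correlation (assumed) | At least one significant interaction, 5 outcomes |
|---|---|
| 0 | about 23% |
| 0.5 | about 19% |
| 0.7 | about 16% |
| 0.8 | about 14% |

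A single outcome gives about 5%, as it should. Allowing for simulation error, the range for correlations of 0.8 to 0.5 is 14–20%, roughly three to four times nominal.

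**3. Could 0.69 be the SD of a Beck or Hamilton total?** Suppose 39 of 40 women score 0 and one scores x. The sample SD is then x/√40.

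- It reaches 0.69 when x = 0.69 × √40 = 4.4.
- If x = 20, it is 20/√40 = 3.2.

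So one woman scoring above about 4.4, with all others at zero, already takes the SD past 0.69. That is hard to square with totals watched for values above 20, in a paradigm meant to bring out symptoms. It is not impossible if nearly everyone scores close to zero.

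**The case against.** Much of the case on the other side stands.

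- **The SDs.** A reader might infer that 0.69 cannot belong to the Beck or Hamilton totals. The documents do not prove that. They give no mean, SD or range for any scale and do not say whether scores were transformed. The women are asymptomatic at entry and expected to have mild symptoms. A safety cut-off may lie far above scores that cluster near zero. The daily ratings could fit these SDs, so the powered variable may already be one of the listed outcomes.
- **The 5% level and the power.** A reader might also infer that neither applies. Each single F test keeps its 5% level; it is the error over the set that is uncontrolled. Power depends on the standardized effect, so a difference in units alone does not void it. The defect is that the outcome supplying that effect is unnamed.
- **A larger error rate.** Counting Groups, Times and interaction on five outcomes (15 tests) gives about 35–47% at correlations of 0.8 to 0.5. That overstates the harm. A Times effect pooled over groups does not address differential response, and the three tests are spelled out only in the sample size paragraph. The interaction-only figure is the relevant one.
- **Purpose.** Section 4 calls the study mechanistic, so several mood scales do less damage than in a confirmatory efficacy trial. This lowers the urgency. It does not remove the need to say which result answers the question.

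**Conclusion.** The point holds in limited form. Section 9 gives at least five mood measures without rank, and Section 10 controls error only among post-hoc t-tests. Over five outcomes the chance of at least one false-positive group-by-time test is about 14–20% rather than 5%. This rests on assumed correlations of 0.8 to 0.5, on counting the daily ratings as one outcome, and on the plan's design of 40 women.

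The SDs of 0.69 and 0.28 belong to no named outcome. They look far too small for Beck or Hamilton totals, but the documents do not exclude it. A reader therefore cannot tell which outcome the 67%, 81% and 60% describe, and those powers do not follow from the stated inputs by the calculations tried. The documents do not support the stronger conclusions that the SDs are impossible for these scales or that the individual tests lose their 5% level.

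**What to change.** In Sections 9 and 10:

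1. Name one primary mood outcome. The natural choice is the measure in the earlier study that supplied 0.69 and 0.28, which the sponsor can identify, provided it is also the measure that best answers the question.
2. Name one primary test at 5%: the group-by-time interaction or a pre-stated contrast within it.
3. Make the remaining mood scales secondary, with Holm adjustment.
4. Label the hormone and o-CRH outcomes secondary or exploratory.
5. State the outcome and unit behind 0.69 and 0.28, recompute the power of the primary test and show the method, and say that it applies to that outcome only. For the interaction, the plan states 60%; its inputs give about 53% with λ = N·f². The recomputation should use the numbers actually planned: Section 3 enrols 40 + 20 + 40 = 100 women, against 40 in Section 10, which is a separate matter to reconcile.

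The change is to wording and needs no extra participants. The secondary scales face a stricter threshold, and the headline power becomes that of the interaction test, 60% or lower. The alternative of keeping five co-equal outcomes with Bonferroni (0.05/5 = 0.01 each) costs more: interaction power per outcome falls to about 28% from the stated inputs, or about 35% if the stated 60% is taken as correct.
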